Protocol Title: Methadone Demonstration Project

NCT03134703

Protocol v5: 02.02.2018

JHM IRB - eForm A – Protocol

- **Use the section headings to write the JHM IRB eForm A, inserting the appropriate material in each. If a section is not applicable, leave heading in and insert N/A.**
- **When submitting JHM IRB eForm A (new or revised), enter the date submitted to the field at the top of JHM IRB eForm A.**

1. Abstract

- a. Provide no more than a one page research abstract briefly stating the problem, the research hypothesis, and the importance of the research.

The Problem:

Infants who are born to mothers taking or abusing opiates frequently suffer from neonatal abstinence syndrome (NAS) after birth. They often have withdrawal symptoms which can be life-threatening if untreated. The American Academy of Pediatrics (AAP) recommends non-pharmacologic treatment as first-line therapy, followed by opioid replacement for severe cases. The pharmacologic treatment usually takes place within the hospital setting. Such approach often incurs prolonged hospitalization and significant financial burden. It also creates barriers to adequate maternal/infant bonding with potential deleterious consequences for the infant's long term emotional and societal outcomes.

The Research Hypothesis: Among Neonatal Intensive Care Unit (NICU) infants diagnosed with NAS and requiring pharmacological treatment, those who are treated with methadone will have a shorter Length of Stay (LOS) of less than 15 days as compared to the average length LOS of 25 days of NAS infants admitted in recent years at Johns Hopkins All Children's Hospital (JHACH) NICU.

The Importance of the Research:

Infants suffering from NAS are historically cared for in the hospital setting and are not discharged home until all narcotic medications have been weaned off. Such prolonged hospital stay invariably equates to prolonged separation of mother and baby. Consequently, infants suffer from the absence of a care giver who could provide constant comforting techniques which are the mainstay of treatment of infants with NAS. This in turn leads to further prolongation of the hospital stay and impaired mother-infant bonding.

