This demonstration project has the potential to improve short and long term outcome of infants suffering from NAS while decreasing the cost of their care. It aims at doing so by 1) reaching out to qualifying mothers prior to delivery; 2) empowering those mothers during their infant hospital stay by further educating them on NAS and means of comforting and easing their infant's withdrawal symptoms; 3) discharging infants home while still on narcotic treatment under very close medical supervision until complete weaning is achieved; 4) ensuring a safe home environment and healthy maternal involvement throughout withdrawal and for a year after cessation of medical treatment.

Principal Investigator: [name], MPH

Application Number: IRB00107690

2. Objectives

Primary Objective: Compare the LOS of NICU infants with NAS treated with methadone with historical data and a comparison group of NICU NAS infants treated with a different narcotic agent.

Secondary Objectives:

- 1) Compare maternal bonding between methadone treated infants and those treated with a different narcotic,
- 2) Assess if methadone treatment leads to decreased maternal depressive symptomatology as compared to treatment with other narcotics;
- 3) Study whether methadone treatments leads to safer transition to home with no readmissions to the hospital within 30 days for NAS-related reasons;
- 4) Compare proportions of children who gain weight (greater than 15% above birth weight) at 30 days of age between methadone treated and non-treated infants;
- 5) Compare the incidence of providing breast milk (> 50% of nutritional needs) at 30 days of age between methadone treated and non-treated infants;
- 6) Assess the age appropriate infant development at 4, 8 and 12 months of age among the methadone treatment group;
- 7) Determine the response percentage of mothers who are screened as eligible by PAR officials and who agree to participate in the demonstration project;
- 8) Assess the drop out percentage of mothers who agree to participate but do not follow through with home discharge for continued care;
- 9) Quantitate the proportion of mothers who feel comfortable with home care of their infant at discharge;
- 10) Monitor the readiness of mothers to assess infant on 3 to 4 hours intervals while at home;
- 11) Determine the compliance rate with the Johns Hopkins All Children's Hospital (JHACH) pediatrician visits.

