NAS is manifested by central nervous system irritability (high pitch and inconsolable crying, irritability and sleep disturbances), autonomic nervous system over-reactivity (sweating, yawning, sneezing), gastrointestinal manifestations (poor feeding, emesis and loose stools) and respiratory distress (tachypnea and nasal congestion) (Finnegan 1975; Finnegan, 1976; Kaltenbach, 1986; Desmond 1975). The standard of care is to treat these infants with a slow taper of opioid but to date there is no established gold standard for that taper (Cochrane, 2010). The lack of high-quality research in the treatment of NAS has led to wide variations in medications and protocols (Patrick, 2014; O'Grady, 2009; Sarkar, 2006) and data on changes in the utilization of NICU resources in the treatment of affected infants are lacking (Tolia, 2015).

For the time frame July 1, 2013 through September 30, 2014, 300 infants with NAS have been cared for at the Johns Hopkins All Children's Hospital (JHACH) NICU with an average length of stay of 30 days. The average length of stay has recently decreased to 22-25 days with implementation of strict management guidelines and protocols. Accounting for an average daily cost of \$2062.50, the burden translates into medical costs averaging \$48,468.75 per infant. With the proposed model involving methadone treatment, we anticipate at most 14 days of care in the NICU at a cost of \$28,875.00, followed by 10 days of home care at an anticipated cost of \$190/day for a total cost of \$30,775. This is an anticipated reduction in cost of \$17,693.75 per patient.

The prolonged stay has other social and medical impacts – including limitation in parental interaction and bonding, exposure to nosocomial infections, and taking up valuable resources both in terms of personnel and equipment. Once discharged home, these infants are often exposed to inconsistent caregiving, family instability, out of home placements, chronic stress, abuse, neglect and poverty – all of which affect their health and development, thus incurring even greater societal costs. To date, there are no published data on the in-home pharmacologic treatment of these infants.

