JHACH NICU Stork Nurses communicate with the Bayfront Baby Place Nurses a minimum of two times per day to check for potential NAS infants and transfers. Such communication readily identifies candidate mother / infant dyads shortly after delivery, and the pre-qualified mother will be approached for consent by a member of the study team (MD or mid-level).

b) **Comparison Group:** Mothers of infants who are admitted to the JHACH NICU with the diagnosis of NAS and who are started on treatment with a narcotic different than methadone, will be identified during the first week of NICU admission. Those mothers will be approached for consent by a member of the study team.

The difference between the two groups is further delineated in the tables below.

NOTE regarding screen failures:

Up to 35% of infants with NAS do not require pharmacological treatment as their symptomatology is controlled by non-pharmacological interventions. Such infants are released home after an observation period of about 7 days. If a patient was consented for either the comparison or methadone group and did not require pharmacological treatment for NAS, these infants will be considered screen failures. Accordingly, there will be no measures of bonding and depression, no outpatient follow-up by either KHC or the JHACH pediatrician and no assessment of development.

Principal Investigator: [name], MPH

Application Number: IRB00107690

Study Design:

Study Schedule of Events:

a) Methadone Treatment Group

Study Intervention	Enrollment	While inpatient	After discharge home on methadone	6 – 8 weeks of age	4 months of age	8 months of age	12 months of age
Informed Consent	X						
Methadone Administration		X ^a	X ^b				
Child Protective Investigator (CPI) clearance of the home		X (prior to discharge)					
Social Work Home Assessment			X (upon discharge)				
Face-to-face teleconferencing			X ^c				
Finnegan scoring		X	X ^b				
Kids Home Care Visit			X ^b		X ^f	X ^f	X ^f
JHACH Outpatient Pediatrician H&P, PE			X ^d				
The Postpartum Bonding Questionnaire (PBQ)		X ^e		X ^f			
Edinburgh Postnatal Depression Scale (EPDS)		X ^e		X ^f			
Ages And Stages Questionnaire (ASQ)					X	X	X

^a Per protocol

^b Twice daily until 48 hours after total weaning of medication is achieved

^c Every 3-4 hours until 48 hours after total weaning of medication is achieved

^d Within 1-2 days after discharge then weekly for 4 weeks until discontinuation of methadone treatment

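### The 25-day historical length of stay is not shown to come from infants who meet the trial criteria, which leaves the historical comparison open to selection bias of unknown net direction

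*Combined protocol and SAP*

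**What the plan says.** Section 1 (Research Hypothesis) proposes that "those who are treated with methadone will have a shorter Length of Stay (LOS) of less than 15 days", set against "the average length LOS of 25 days of NAS infants admitted in recent years". The Primary Objective in section 2 names two comparators, historical data and a concurrent group: it is to "Compare the LOS of NICU infants with NAS treated with methadone with historical data" and with infants given another narcotic.

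Section 3 (Background) describes a 15-month series, July 2013 to September 2014, in which "300 infants with NAS have been cared for" with a mean stay of 30 days. It continues: "The average length of stay has recently decreased to 22-25 days with implementation of strict management guidelines and protocols". No limit on gestation, birth weight, transfer time, concurrent illness or drug treatment is stated for any of these averages.

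Section 4 requires infants in both groups to be at least 37 weeks and 2.5 kg, transferred within 72 hours of birth, and without major anomalies or major illness. The methadone group must also come from compliant, dose-stable, prescreened mothers at Operation PAR, with no known child-protection concern and no non-opiate drug of abuse on the maternal screen. The note on screen failures says that "Up to 35% of infants with NAS do not require pharmacological treatment" and that these infants leave after about 7 days. They are dropped from both groups.

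Section 6c tests LOS against the concurrent group only. It uses the historical 25 days as the expected mean of that group and describes no historical analysis.

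**The concern.** A historical control is informative only if its infants resemble those in the trial. Here one side is tightly selected and the other is described only as NAS infants from recent years. Selection alone could then produce or hide a difference in LOS, and nothing in the plan would allow a reader to tell. This matters because the only stated hypothesis is framed against the historical figure, and the primary objective lists historical data first.

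**Working it through.** **1. The plan's own figure.** Section 6c states that 25 per group gives 80% power for a difference of 4 days with SD 5 and alpha 0.05 (taken as two-sided).

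- Normal approximation: n = 2 × (1.96 + 0.84)² × 5² / 4² ≈ 24.5, so 25 per group. Power at n = 25 is 80.7% (79.1% by the exact t calculation).
- The statement reproduces. The 25-day mean does not enter the formula, so changing the benchmark leaves the sample size unchanged.

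**2. Is the historical population known?** Two sets of facts point in different directions.

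- 300 infants in 15 months is 300 / 15 × 12 = 240 a year. The Accrual paragraph gives an average of 131 a year needing drug treatment, and 131 / 240 = 55%. If the periods are comparable, the 30-day series included untreated infants.
- The hypothesis is framed for infants needing drug treatment. The Accrual paragraph uses the same recent-years phrase for treated infants, and section 6c applies 25 days to a group that excludes untreated infants. The 25 days may therefore be a treated-only figure.
- The cost estimate in section 3 implies $48,468.75 / $2,062.50 = 23.5 days, the midpoint of 22 and 25. So 25 is not the only current value in use.

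**3. Which way could restriction move 25 days?**

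(a) Removing untreated infants, if they are in the series. Treated mean = (25 − f × 7) / (1 − f), where f is the untreated share:

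| f | Treated mean (days) |
|---|---|
| 10% | 27.0 |
| 20% | 29.5 |
| 35% (the plan's upper limit) | 34.7 |

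Here 25 days would be too short, which works against methadone.

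(b) Removing ineligible infants who stay longer. The documents give no figures, so both inputs are assumptions: an ineligible share s of 10% to 30% and an excess stay e of 5 to 15 days. Eligible mean = 25 − s × e, from 25 − 0.10 × 5 = 24.5 down to 25 − 0.30 × 15 = 20.5 days. Here 25 days would be too long, which favours methadone.

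**4. How much would a mismatch matter?** The plan specifies no historical test, so assume a two-sided one-sample t-test against a fixed 25 days with n = 25, SD 5 and no true effect. The standard error is 5 / √25 = 1 day and the critical value is t(24) = 2.064. If eligible infants on usual care would really stay b days less than 25, the non-centrality is −b:

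| b (days) | Chance of falsely declaring a shorter stay |
|---|---|
| 0 | 2.5% |
| 1 | 15.9% |
| 2 | 48.4% |
| 3 | 82.1% |

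If the benchmark is too short, the error is conservative: at 1 day too short the chance falls to 0.2%. If the full 10-day gap (25 against 15) were observed, a bias of about 10 − 2.064 = 7.9 days would be needed to remove significance.

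**The case against.** The strongest reply is that the only specified LOS test is against a concurrent group that shares the gestation, weight, transfer-time and illness criteria and must be drug-treated. The benchmark affects neither that test nor its power, and the study is declared a non-randomized feasibility study. All of this stands, and it confines the harm to the historical comparison. It does not remove the point, because the plan names that comparison in its hypothesis and primary objective.

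It is also fair to say that the 25-day cohort may already be limited to treated infants. In that case the untreated-infant component disappears, but the other criteria remain unmatched.

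Two stronger readings are tempting, and the documents support neither.

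- A reader might infer that the reference is uncertain by 6 to 10 days, from 34.7 − 25 = 9.7 and 25 − 18.7 = 6.3, where 18.7 = 0.65 × 25 + 0.35 × 7. The 18.7 arises only if 25 days is already treated-only. Then 25 is the relevant figure for a treated-infant hypothesis and this source shifts nothing. The 34.7 uses the maximum untreated share, exceeds even the 30-day mean reported before LOS fell, and makes 25 days conservative.
- A reader might add a time trend of 5 to 8 days from the fall from 30 to 22-25. The hypothesis uses 25, which lies inside the later range, so the fall is already reflected. The ambiguity left is at most 22 against 25.

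**Conclusion.** The point holds for the historical comparison only. Its population is not shown to meet the trial criteria, and no restriction, matching or adjustment is planned. The net direction of any bias cannot be determined from the documents, so it would be wrong to say that the benchmark is known to favour methadone or that it certainly covers all NAS admissions.

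On size, a benchmark 1 to 3 days too long would give about a 16% to 82% chance of a false claim of shorter stay. A 3-day error is within the plan's own 22-25 range. These probabilities rest on the assumed one-sample test, n = 25, the plan's SD of 5 and no true effect. A very large observed gap would be much more robust. The concurrent-group test and the sample size are unaffected by the 25-day mean.

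**What to change.** From the site's own records, define the historical cohort as drug-treated NAS infants admitted after the current management guidelines began who meet the comparison group's gestation, birth-weight, transfer-time and exclusion criteria. The consent criterion cannot apply to a records query. Those criteria alone would leave the Operation PAR, maternal-compliance and polydrug selection of the methadone group unmatched, and child-protection status only partly matched. So restrict or stratify further by Operation PAR and polydrug status where recorded, and state what could not be matched.

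Report the cohort's dates, n, mean and SD. Use that single mean in the hypothesis and the historical comparison, and check the assumed SD of 5 days against the observed SD, since the SD does enter the sample size. State in section 6c how the historical comparison will be made, and that it is supportive to the concurrent one.

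The cost is one records query. The benchmark may become less favourable to methadone. Enrolment and treatment do not change.

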This application is for a demonstration study, funded by the State of Florida Department of Health, using oral methadone to treat NAS both inpatient and outpatient in a specified infant population. The outpatient administration of oral methadone will be provided solely and directly by JHACH Kids Home Care registered nurses who are adequately trained and skilled in the recognition and management of NAS. Methadone will be administered at Operation PAR or at the parent home. Operation PAR, Inc. is a Detoxification Program Treatment Center in Largo Florida, and offers halfway housing as well as residential treatment options for clients in opioid treatment program. Operation PAR has agreed to assist in the identification of potential participants as well as allow JHACH Kids Home Care RNs to perform study related interventions at their site.

Current Experience with Procedures/Drugs:

JHACH operates one of Florida's largest neonatal intensive care units. With 97 beds, the JHACH NICU is dedicated to the outcomes of infants encompassing all types of illnesses from prematurity, neurological issues, surgical and medical needs, and neonatal abstinence syndrome (NAS). The staff in the NICU at JHACH (nurses and neonatal nurse practitioners) have been trained in the standardized scoring of NAS symptoms using the Modified Finnegan Neonatal Abstinence Severity Scoring tool (Finnegan, 3rd edition, pp. 1367-1378, 1992) and have been successfully applying it for the NAS population, averaging more than 100 infants per year. Even though morphine with clonidine adjunct therapy are the current standard of care at JHACH NICU, inpatient methadone was extensively and successfully used by JHACH for the treatment of NAS until 2010. The shift in protocol resulted from reasons unrelated to the effectiveness nor safety of methadone, and related instead to an attempt to modify the LOS.

This demonstration project will provide an opportunity to transition care of these infants to home, thus allowing for better care for the infant and improved neonatal outcome.

Principal Investigator: [name], MPH

Application Number: IRB00107690

Other Relevant Information to Justify Research

Summary:

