^e After initiation of methadone treatment and prior to discharge during the weaning phase of narcotic treatment

^f Home visit or phone interview

Principal Investigator: [name], MPH

Application Number: IRB00107690

Comparison Group:

Study Intervention	Enrollment	While inpatient	6 – 8 weeks of age
Informed Consent	X		
The Postpartum Bonding Questionnaire (PBQ)		X ^a	X ^b
Edinburgh Postnatal Depression Scale (EPDS)		X ^a	X ^b

^a After initiation of standard of care narcotics for treatment of NAS and prior to discharge during the weaning phase of narcotic treatment

^b Administered either through a home visit by Kids Home Care or via a phone interview conducted by a study team member

Routine (usual) care for infants born to mothers with a history of opiate use: All infants have routine scoring with the modified Finnegan scoring tool approximately every 3 to 4 hours per standard of care for signs of NAS. Infants will be managed with comfort, non-pharmacological measures. Initiation of medical treatment will take place when 2 consecutive Finnegan scores are > 8. Escalation of treatment and weaning will follow set protocols. Vital signs, blood pressures and cardiorespiratory monitoring follow the NICU standard of practice. Outpatient neurodevelopmental follow-up is offered at 1 and 2 years of age.

Comparison Group:

The comparison group of mother/baby dyads will receive standard of care treatment. The study interventions in this group are limited to the bonding and depression assessments. All other data required for analysis of the study aims can be abstracted from the baby's medical record as it is part of standard clinical care.

Methadone Treatment group:

A. Infant participants will receive the following services not part of the standard of care at JHACH:

- a) Initiation of the commercially available methadone treatment instead of morphine as pharmacologic treatment (see methadone treatment below);
- b) Maternal education on recognizing signs and symptoms of withdrawal as well as understanding and performing adequate Finnegan scoring. Specifically, mothers will be taught how to demonstrate tone and tremors on Physical exam.
- c) Provision of close psychological and emotional support to mothers

Principal Investigator: [name], MPH

Application Number: IRB00107690

- d) Facilitation of prolonged maternal physical presence at her infant's bedside

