It is standard of care for infants discharged from the JHACH NICU to see their primary care provider (PCP) within a day or two of discharge. Follow-up will be provided by an IRB approved study team JHACH Pediatrician, and will take place within one or two days after discharge then weekly for 4 weeks after discontinuation of methadone treatment.

G. Off-treatment Criteria:

Principal Investigator: [name], MPH

Application Number: IRB00107690

Off-treatment is defined as an infant who no longer qualifies for discharge home on methadone – i.e. requiring adjuvant pharmacological therapy or re-admission to the hospital while still on methadone

1. Addition of adjuvant therapy:

It is common for infants suffering from NAS to require the addition of an adjunct therapeutic agent for control of symptoms. This second-line agent varies among institutions but consists often of phenobarbital.

If demonstration project participants have uncontrolled NAS symptoms (defined as a 24-hour Finnegan score average ≥ 11 despite comfort measures and maximal methadone dosing – i.e. 0.1 mg/kg given every 4 hours), the infant will be placed on phenobarbital, the standard of care at JHACH NICU. Such infant will be off-treatment from the study i.e. will not qualify for subsequent discharge home prior to discontinuation of methadone. Maternal assessments of bonding and depression will remain ongoing. There will be no home nursing visits.

2. Re-admission to the JHACH NICU:

It is common for infants suffering from NAS not to tolerate weaning off medication. Re-escalation during that phase is common. If during the weaning phase, infant's Finnegan scores are > 8 on 2 consecutive scores despite comfort measures, the dose of methadone will be increased to the previous dose at which the patient's symptoms were well controlled.

If an infant requires consecutive re-escalation of medication with no control of symptoms (i.e. 24 hour Finnegan scores > 6), such infant will be re-admitted to the hospital.

- for infants who were discharged home on a dose of methadone that is < 0.04 mg/kg, such infant will be re-admitted to the hospital if consecutive re-escalation of methadone are required and infant reaches a dose of 0.05 mg/kg.

- for infants discharged home at a dose of 0.04 mg/kg, who do not tolerate weaning at home and who require dose escalation, the dose will be increased in 2 increments per protocol to a value of 0.07 mg/kg before re-admission to the hospital.

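### The objectives name methadone as the exposure, but only the methadone group also gets maternal support and discharge on treatment: no difference can be credited to the drug, and even a programme contrast is open to selection

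*Combined protocol and SAP*

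**What the plan says.** **Objectives.** The hypothesis in section 1 predicts a LOS below 15 days in infants treated with methadone, against a recent JHACH average of 25 days. The primary objective in section 2 begins "Compare the LOS of NICU infants with NAS treated with methadone with historical data and a comparison group of NICU NAS infants treated with a", and its last words name another opioid as the comparator. Secondary objective 1 compares bonding between the same drug-defined groups. Secondary objective 2 is to "Assess if methadone treatment leads to decreased maternal depressive symptomatology as compared to treatment with other narcotics". Secondary objective 3 asks whether methadone leads to a safer transition home. Secondary objectives 4 and 5 contrast methadone-treated with non-treated infants on weight gain and breast milk.

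**What each group receives.** Study Procedures, Methadone Treatment group, list A, sets out services beyond JHACH standard care. Methadone in place of morphine is item a. Then come maternal education (b), "Provision of close psychological and emotional support to mothers" (c), "Facilitation of prolonged maternal physical presence at her infant's bedside" (d), discharge home while still on methadone (e), twice-daily nurse visits (f), a tablet with teleconferencing every 3 to 4 hours (g, h) and a social work home assessment (i). The comparison group has standard care: "The study interventions in this group are limited to the bonding and depression assessments".

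**Analysis.** Section 6c plans a t-test or Wilcoxon test for LOS, t-tests for the PBQ and EPDS, and chi-squared or Fisher tests for readmission and weight gain. None is adjusted.

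**Adjunct.** Section 3, Current Experience with Procedures/Drugs, says that "morphine with clonidine adjunct therapy are the current standard of care at JHACH NICU". Study Procedures, G. Off-treatment Criteria, says that after failure of maximal methadone "the infant will be placed on phenobarbital, the standard of care at JHACH NICU".

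**The concern.** The question is posed about a drug, while the groups differ by a drug plus a package of care, and the package acts on the outcomes measured. Psychological support bears directly on the EPDS, and time at the bedside on the PBQ. For LOS the protocol gives the mechanism itself. Section 1 treats a caregiver's comforting as central to treatment and says of its absence: "This in turn leads to further prolongation of the hospital stay and impaired mother-infant bonding". Discharge before weaning is complete shortens LOS by definition, whichever opioid is used.

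If the results are read in the terms of the objectives, methadone could be credited with a better EPDS score that came from support, or with a shorter stay that came from moving the last part of treatment to the home. A unit that then changed its opioid without the package would be acting on a finding the trial did not make.

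**Working it through.** **1. The plan's own sample size.** Inputs from section 6c: 25 dyads per group, difference 4 days, SD 5 days, alpha 0.05, power 80%. Two-sided testing is assumed, since sidedness is not stated.
- n per group = 2 × (1.96 + 0.84)² × 5² / 4² ≈ 24.5, so 25.
- Standard error = 5 × √(2/25) = 1.414. Power by normal approximation = Φ(4/1.414 − 1.96) = 0.807; by the exact t-test, 0.791.

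The stated figure reproduces. The problem is one of attribution, not arithmetic.

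**2. How much of the projected saving is change of setting?** Inputs from section 3, The scope of the problem.
- Current care: $48,468.75 / $2,062.50 per day = 23.5 days.
- Programme, NICU part: $28,875 / $2,062.50 = 14 days.
- Programme, home part: ($30,775 − $28,875) / $190 = 10 days.
- Projected LOS saving: 23.5 − 14 = 9.5 days. Days moved home: 10. Total care: 24 days against 23.5.

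Section 3 gives current LOS as 22 to 25 days. At 22, the saving is 8 days against 10 moved home; at 25, it is 11 against 10. The saving not matched by home days therefore lies between −2 and +1 day. The 14 days are described as a maximum, so total care could fall below 24.

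**3. The same drug and schedule, with only the discharge rule changed.** Inputs from Table 2 (minimum doses), C. Discharge home and E. Home observation.
- Step 1: 8 doses × 6 h = 2 days. Steps 2 to 7: 6 × (2 × 12 h) = 6 days. Step 8: 1 day. Total 9 days, or 12 with 72 hours of observation.
- The Step 4 dose is reached after 2 + 1 + 1 = 4 days. If Steps 2 to 4 count as the three days of weaning, discharge comes after 5 days.
- Treatment moved home: 9 − 4 = 5 or 9 − 5 = 4 days. With observation: 8 or 7 days.

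On the fastest schedule, the discharge rule alone moves at least the 4 days for which the study is powered.

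**4. What the planned test would show if the opioid added nothing.** Exact t-test, 25 per group, SD 5, two-sided 0.05:

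| Assumed non-drug shift in LOS (days) | Probability of significance |
|---|---|
| 1 | 0.107 |
| 2 | 0.283 |
| 3 | 0.547 |
| 4 | 0.791 |
| 5 | 0.934 |
| 7 | 0.998 |

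This is the ordinary power curve. The documents give no size for the effect of education, support or bedside presence, so the rows for 1 to 4 days only illustrate. At the projected 9.5 days the probability is effectively 1.

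**5. Are the groups otherwise comparable?** General Design Issues describes a non-randomised, unblinded study. Under section 4 only the methadone group must have a mother who is under Operation PAR care, resident in one of two counties, judged compliant, stable on her own dose, prescreened by the team and free of known child-welfare concerns. Only that group excludes infants whose mother's drug screen at delivery shows a drug of abuse other than opiates. The comparison group's exclusion of infants bound for state custody is a partial counterpart to the child-welfare criterion; the others have none.

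**The case against.** The best defence is that the protocol already describes a programme. The second paragraph of the abstract says the project works through outreach, maternal education, discharge on treatment and home support. Section 3 chooses methadone partly because its dosing interval suits home use, and the extra services are listed openly. 'Methadone treated' can be read as a group label, the primary objective and secondary objective 1 say only 'compare', and no sentence says a difference will be credited to the opioid alone. This stands in part: misattribution is a risk created by the wording, not a declared intention. But the hypothesis and objectives are what the results will be read against, and two of them say that methadone leads to the outcome. That methadone makes home care feasible makes it a component of the programme and gives no reason for it to lower an EPDS score by itself.

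Comparison mothers are not wholly without support. Standard care includes comfort measures, and the safety plans for the PBQ and EPDS offer counselling to any woman with a high score. That is a response to a score, not the package in list A.

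A reader might infer more than the documents support:
- **That the design at least answers the programme question.** It does not: allocation is non-random, eligibility differs and the tests are unadjusted.
- **That every objective claims a causal effect against another narcotic.** The hypothesis compares with a historical average, and secondary objective 3 names no comparator, although section 6 compares readmission between the groups.
- **That adjunct practice differs between the groups.** One statement pairs clonidine with morphine and the other concerns failure of methadone, so a real difference is not established.
- **That methadone has no effect on LOS.** The cost model is a projection, and it shows only that the saving does not depend on one.

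**Conclusion.** The point holds as a mismatch between objectives and design. No difference in LOS, PBQ or EPDS can be attributed to methadone itself, because the drug is never separated from the maternal services or from discharge on treatment. For LOS the dominant non-drug element is the discharge rule: about 10 of the projected 9.5 days saved are days moved home, leaving between −2 and +1 day across the protocol's range for current LOS. This rests on the cost model in section 3 and on reading current practice as discharge only after weaning, which section 1 describes as historical practice. For the PBQ and EPDS the direction is clear but no size can be given. A programme-level difference would also be an association open to selection bias. The sample size calculation is unaffected.

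**What to change.** 1. In sections 1 and 2, reword the hypothesis, the primary objective and secondary objectives 1 to 5 as a comparison of outcomes between dyads in the methadone-based hospital-to-home programme and dyads receiving JHACH standard inpatient care. Replace 'leads to' with 'is associated with' in secondary objectives 2 and 3.
2. In section 6, state that no difference will be attributed to methadone itself, and that a programme effect is subject to selection bias. Rewording does not remove that bias; it keeps the conclusion within what the design supports.
3. Report total days of opioid treatment (inpatient plus home) beside LOS in both groups. This shows how much of a LOS difference is change of setting, though it does not isolate the drug.
4. Separately, reconcile section 3 with G. Off-treatment Criteria on which adjunct is the JHACH standard, and record adjunct use in both groups.

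The cost is wording in three sections, one added summary and one data field; comparison-group data can come from the medical record the protocol already plans to abstract. Arms, visits and sample size do not change. The downside is that the trial gives up a drug-specific claim, which it could not have supported.
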